12 PHARMACOVIGILANCE

- As this is not a clinical trial of a medicinal product and the intervention, and its delivery, are considered safe and already in universal use we do not anticipate any adverse reactions due to the trial intervention (use of donor breast milk products). However, this is a very high risk patient group and some infants may develop serious complications e.g. sepsis, and some may die. We will record all serious adverse events (SAE). Serious adverse events that may occur include:
- Outcomes recorded and reported as part of the study: necrotising enterocolitis (NEC), sepsis, intraventricular haemorrhage, periventricular leukomalacia, retinopathy of

- prematurity, chronic lung disease, feeding intolerance (number of days when nil by mouth i.e. no enteral intake and need for parenteral nutrition), antibiotic exposure (number of days on which an antibiotic was administered) and death.
- 719 Outcomes that commonly occur in this population but that will not be specifically 720 recorded or reported as part of this study include: abnormal electrolytes, bone 721 chemistry, liver functions tests or other routine biochemistry or haematology; 722 transfusion of blood or related products; complications related to use of intravenous 723 catheters (e.g. misplacement or malfunction); presence of and/or treatment for a patent 724 ductus arteriosus; requirement for surgery and/or provision of an intestinal or airway 725 stoma, intraventricular shunt; vomiting, gastro-oesophageal reflux, constipation, 726 diarrhoea, skin or nappy rash.

731

732

733

734

735

736

737

738

739

740

741

742

743

744

745

728 13 STATISTICAL CONSIDERATIONS

729 13.1 Sample size calculation

730 13.1.1 Gut bacteria

- Using 16S rRNA bacterial profiling data we will conduct alpha and beta diversity analysis. Based on previously published data by our group[12,13] a Shannon Diversity Index alpha diversity of <1 is representative of infants in the initial weeks of life where the microbiome is undeveloped; a Shannon Diversity Index of >1.5 is representative of infants immediately prior to neonatal unit discharge where the gut microbiome is more developed and risk of gut microbiome mediated disease is significantly reduced. Based on these findings a sample size of 24 in each group (48 in total) is required to achieve over 95% power detect a 0.5SD difference in diversity index. By processing 40 samples in each group we will reach this power for true significance of alpha diversity analysis and note from previous analysis that that this number is also sufficient for beta diversity analyses, including but not limited to UniFrac distance, clustering (PAM and DMM), correlation (CCLasso), ordination analysis (PCA and PCoA), and determining significant differences between the relative abundance of different genera.
- 746 13.1.2 Body composition

Supplementary materials Effect of an exclusive human milk diet on the gut microbiome in preterm infants; a randomised clinical trial

We will compare proportions of key taxa e.g. proteobacteria, firmicutes etc., as well as

numbers and presence of key species including lactobacilli, bifidobacteria and staphylococci.

- In our most recent work in preterm infants born at <31 weeks gestational age, the mean (SD)
- of non-adipose tissue mass was 2.41 (0.46) kg (Uthaya et al. 2016)[14]. A sample size of 20
- 549 babies per group will have 80% power at the 5% significance level (2-sided) to detect a 0.42
- 750 kg between-group difference in non-adipose tissue mass assessed by whole body Magnetic
- 751 Resonance Imaging using protocols previously described[15,14].

752 13.1.3 Metabolome

- 753 Stool VOC analysis identifies several individual compounds; our collaborators show an
- average 31.3±10.5 (Mean and SD) VOCs were identified per sample [16]. With n=40 infants
- per group we will have 85% power to detect an increase in 5 VOCs between intervention and
- standard groups. Urinary 1H NMR studies are limited in preterm infants. However, highly
- 757 significant differences in spectra (p<0.005) were detected between adults born preterm
- 758 (n=19) and term (n=17). The differences observed were in key metabolites such as
- 759 trimethylamine, an end product of choline metabolism by gut bacteria[17].

760 13.1.4 Urinary and stool markers of gut integrity or inflammation

- 761 Intestinal fatty acid binding protein (iFABP) is highly correlated with gut inflammation,
- represents damage and release of this protein from gut enterocytes, and has been proposed as
- a biomarker of gut health and NEC. In a recent case control study (with n=14 pairs)
- 764 significant differences were detected in infants (compared to well controls) up to 7 days
- 765 before early NEC stage 1 (p=0.005). Because the data are skewed it is not possible to use
- them for a traditional power calculation but typical values were 4ng/ml (range 2-7ng/ml) in
- 767 control infants and 15ng/ml (range 6-42ng/ml) who subsequently developed early NEC.
- 768 Assuming gut inflammation in infants receiving cow's milk derived products was only
- increased slightly (to 6ng/ml) and that the SD in control infants was 1.5ng/dl, the study would
- have 85% power to detect such a small increase with just n=20 infants per trial group[18].
- 771 We will also explore the use of stool calprotectin as an additional marker of gut inflammation
- but there are insufficient data to perform a power calculation.

773 13.1.5 Plasma amino acids

- 5774 Standard analyses of 9 essential and 9 non-essential amino acids. Plasma levels of threonine,
- valine, phenylalanine, methionine and tryptophan are typically higher when infants are fed
- whey based hydrolysed cow's milk protein, which is the source of protein in commercially
- available cow's milk based breast milk fortifiers. We will compare total essential and non-

essential levels. Although reference data in this group of infants are not available for total levels, typical tryptophan levels are 30±12umol/l. 20 infants per group, would therefore give a power of 83% to detect a clinically important increase from 30umol/l to 40umol/l.

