1. PROTOCOL SUMMARY

Title (Acronym)	In teractions between the di et and g ut microbes, metabolism and body composition in preterm infants (INDIGO)
Study centres	Newcastle Royal Infirmary and Chelsea and Westminster NHS Foundation Trust (Imperial College London). Additional sites may be added
Study objectives	To evaluate whether an exclusive human milk diet compared with exposure to cow's milk-based products results in differences in a) gut bacteria (types and diversity, b) stool and urine metabolites and c) body composition
Study design	Randomised open label, controlled trial
Study population	 Inclusion criteria Preterm infants born below 30 completed weeks of gestation (≤ 29 weeks and 6 days) <72 hours age Written informed consent from parents Exclusion criteria Major congenital or life-threatening abnormalities Inability to randomise within 48 hours of birth Exposure to bovine milk product prior to randomisation Likelihood of transfer to another hospital before 34 weeks postmenstrual age
Interventions	• Exclusive human diet (human donor milk and human milk-based fortifier: 'Prolacta RTF 26' and 'Prolacta 6')
Route of administration	Enteral
Target number of patients	At least 100 patients to provide ~80 evaluable infants in total with stool samples for microbiome analysis at 34w PMA
Randomisation	 Using minimisation incorporating the following variables: hospital site, gestation (<25 weeks: ≤24 weeks and 6 days), and multiple birth status Secured, password protected web-based randomisation using minimisation algorithm (www.sealedenvelope.com or similar)
Primary outcomes	 Microbiota: gut bacterial diversity, proportions of specific taxa, e.g. Bifidobacteria species Body composition; adipose tissue mass and non-adipose tissue mass assessed using whole body magnetic resonance imaging (MRI) at term (37-42 weeks postmenstrual age)
Secondary outcomes	Metabolome: Gut derived metabolites and markers of gut function; metabolites include stool Volatile Organic Compounds (VOC, using Gas Chromatography MS), and urine (e.g. using 1H NMR and/or Liquid Chromatography MS); markers of gut health may include those measured in the stool (e.g. calprotectin) and urine (e.g. intestinal fatty acid binding protein, iFABP) Feed and nutrition related outcomes Healthcare resource use Neonatal morbidities and clinical outcomes Adipose tissue volume and distribution
Duration of trial intervention	To 34 weeks postmenstrual age

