9.5. Randomisation

Infants will be randomised using minimisation incorporating the following variables: hospital site, gestation (<25 weeks: ≤ 24 weeks and 6 days), and multiple birth status; this will be held and coordinated by the Newcastle research team using an internet based secured randomisation system, and will include strata for hospital site, gestation (<25 weeks and ≥ 25 weeks gestation), and multiple birth status. Contact and allocation will be by password protected internet access. Infants will be allocated to either standard diet (control) or the exclusive human milk-based diet (intervention). Multiples (twins and higher order) will be randomised independently.

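### Section 13.1.3 claims 85% power for a 5-VOC difference with 40 infants per group; a two-group comparison on its own inputs gives about 56% (two-sided 5%) or 68% (one-sided 5%)

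*Protocol*

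**What the plan says.** Protocol section 13.1.3 (Metabolome) cites earlier work by collaborators in which an "average 31.3±10.5 (Mean and SD) VOCs were identified per sample". It then gives the power claim: "With n=40 infants" "per group we will have 85% power to detect an increase in 5 VOCs between intervention and" standard groups. No alpha, sidedness, test or formula is given for this calculation.

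Three other places bear on it:

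- Section 13.1.2 (Body composition) has the only explicit significance level in the sample size section: "80% power at the 5% significance level (2-sided").
- Section 9.5 (Randomisation) fixes a design of two parallel arms: "Infants will be allocated to either standard diet (control) or the exclusive human milk-based diet (intervention").
- The Protocol Summary sets the target: "At least 100 patients to provide ~80 evaluable infants in total with stool samples for microbiome analysis at 34w PMA". The 40 per group is thus already net of expected losses.

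The stool VOC profile is listed as a secondary endpoint in section 8.2 (8.2.1.1).

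**The concern.** The difference of 5 is a little under half of the stated SD (5/10.5 = 0.476). Forty per arm is well short of what a two-group comparison usually needs for 85% power at an effect of that size, so the claim looked too favourable by a wide margin.

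At stake is how a result on the number of VOCs is read. A reader who accepts 85% will take the chance of missing a true difference of 5 to be 15%. If the real figure is two to three times that, a non-significant count says much less about a 5-VOC effect than the protocol implies. This is also the only power figure given for the metabolome: the urinary NMR text that follows it in 13.1.3 reports a finding in adults and states no power.

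**Working it through.** **Inputs.** Difference 5 VOCs, SD 10.5 and n = 40 per group (all section 13.1.3); two independent arms (section 9.5). Assumed, because 13.1.3 is silent: 5% two-sided, taken from 13.1.2, with 5% one-sided as a variant; one VOC count per infant.

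**1. What reproduces the stated 85%.** Using the standard error of a single mean:

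- SE = 10.5/√40 = 1.660
- 5/1.660 = 3.012
- Power = Φ(3.012 − 1.960) = Φ(1.052) = 85.4% (normal). The one-sample t version gives 83.6%.

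Entering 80 as the number per group gives the same standard error, because 10.5 × √(2/80) = 10.5/√40 = 1.660. The result is 85.4% (normal) or 84.9% (two-sample t). The two routes cannot be told apart from the result.

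**2. The two-group calculation.**

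- SE = 10.5 × √(2/40) = 2.348, which is √2 times the figure above
- 5/2.348 = 2.13
- Two-sided 5%, normal: Φ(2.13 − 1.96) = 56.7%
- One-sided 5%, normal: Φ(2.13 − 1.645) = 68.6%

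With the noncentral t distribution on 78 degrees of freedom:

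| Alpha | Power, 40 per group |
|---|---|
| 5% two-sided | 55.7% |
| 5% one-sided | 67.9% |
| 10% two-sided | 68.0% |
| 20% two-sided | 79.9% |

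Even a two-sided alpha of 20% does not reach 85%.

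**3. What 85% would require (t test).**

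| | Two-sided 5% | One-sided 5% |
|---|---|---|
| Infants per group for a difference of 5 | 81 | 65 |
| Difference detectable with 85% power, 40 per group | 7.1 VOCs | 6.4 VOCs |
| Difference detectable with 80% power, 40 per group | 6.7 VOCs | 5.9 VOCs |
| SD at which 40 per group gives 85% for a difference of 5 | 7.4 | 8.3 |

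If 100 infants were recruited and all were evaluable, 50 per group would give 65.5% two-sided or 76.4% one-sided.

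**4. Cross-check within the protocol.** The body composition figure in 13.1.2 (0.42 kg, SD 0.46, 20 per group) comes back as 80.3% with a two-sample, two-sided 5% t test, matching the stated 80%. The tryptophan figure in 13.1.5 (30 to 40, SD 12, 20 per group, stated 83%) comes back as 82.7% with a two-sample one-sided 5% t test. Each of these matches an ordinary two-sample test; the VOC figure does not.

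**The case against.** **Alpha and sidedness are not given.** Section 13.1.3 speaks of an increase, and the tryptophan figure fits a one-sided test, so one-sided may have been meant here too. This stands as a reason to report both figures and to label 56% as resting on a borrowed level. It does not rescue 85%: one-sided power is 68%, still 17 points short.

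**The SD is per sample, and stools are collected daily (11.2.1).** Averaging several samples per infant would reduce the SD. Two uncorrelated samples give 10.5/√2 = 7.42 and 84.5% power, two-sided. With a within-infant correlation of 0.5, the SD is 10.5 × √0.75 = 9.09 and power is 68%. The protocol states no averaging or correlation for VOCs and its calculation counts infants, so this is no support for the printed figure. The recalculation does assume one value per infant and should say so.

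**The cause is not documented.** A reader might infer that the authors left out one group's variance. The protocol shows no formula, and using the total as the per-group number gives the same answer, so only consistency with either slip can be claimed.

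**The consequence is narrow.** A reader might infer that the whole metabolite objective, or the trial itself, is underpowered. The protocol does not support that. Stool VOCs sit beside urine metabolites and gut markers (6.2), and section 11.4.3 also prepares abundance summaries of acids, alcohols and esters, to which the power for a count does not apply. The target of about 80 evaluable infants is tied to the microbiome analysis, and the trial calls itself mechanistic (4.4) and exploratory (14). This objection stands and limits the weight of the point.

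**Conclusion.** The stated 85% is wrong on the protocol's own inputs, and nothing elsewhere in the protocol corrects it. With SD 10.5, a difference of 5, 40 per group, independent arms and one value per infant, power is about 56% at two-sided 5% and about 68% at one-sided 5%. The shortfall is 29 or 17 percentage points. The type II error for a true 5-VOC difference is about 44% or 32%, where 85% power implies 15%.

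The arithmetic is certain given those inputs; which of the two figures applies depends on an alpha and sidedness that 13.1.3 leaves out. The point is a should-fix: it concerns the count of VOCs identified, one secondary metabolomic measure, and has no bearing on the recruitment target or the primary outcomes.

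**What to change.** In section 13.1.3, state the alpha, the sidedness and that one value per infant is assumed, and replace the power sentence with, for example:

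*With 40 infants per group and SD 10.5, the study has 56% power (two-sided 5%) to detect a difference of 5 in the number of VOCs identified, and 80% (85%) power to detect a difference of 6.7 (7.1) VOCs.*

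If a one-sided 5% test was intended, say so and give 68% for 5 VOCs, with 80% (85%) power for 5.9 (6.4). If the authors relied on a smaller SD, for instance from averaging repeated stools, give that SD and its basis.

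The cost is one sentence and a less favourable printed figure. Recruitment, sampling, endpoints and analysis stay as they are.

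### The 83% power for tryptophan (13.1.5) is about 73% at two-sided 5%, and the 85% for iFABP (13.1.4) does not follow from its printed inputs

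*Protocol*

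**What the plan says.** Section 13.1.5 gives the spread as "typical tryptophan levels are 30±12umol/l" and concludes that "20 infants per group, would therefore give a power of 83% to detect a clinically important increase from 30umol/l to 40umol/l". It plans to compare total essential and total non-essential amino acids. Tryptophan is used for the calculation because reference data for the totals are not available.

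Section 13.1.4 gives the iFABP inputs. In control infants "typical values were 4ng/ml (range 2-7ng/ml) in". For the cow's milk arm, the assumption reads "increased slightly (to 6ng/ml) and that the SD in control infants was 1.5ng/dl, the study would". The claim drawn from these inputs is that the trial will "have 85% power to detect such a small increase with just n=20 infants per trial group". Just before this, the section says of the source study: "Because the data are skewed it is not possible to use" them for a conventional power calculation.

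Neither section states a significance level or whether the test is one- or two-sided. The only statement of either in 13.1 is for body composition in 13.1.2, where 20 "babies per group will have 80% power at the 5% significance level (2-sided) to detect a 0.42" kg difference. The hypothesis in section 5 speaks of differences between the diets, without direction.

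**The concern.** A power figure can be read only with its test level. A reader who meets 80% in 13.1.2 and 83% in 13.1.5 will take them to be on the same scale and conclude that tryptophan is slightly better powered than body composition. If the 83% holds only for a one-sided test, the order reverses and tryptophan falls below 80%.

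This matters for interpreting a null result. Plasma amino acid profiles are listed in 8.1.3.2 among the primary endpoints for Newcastle, and this is their only power statement. The protocol itself calls the 10 umol/l difference clinically important.

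The iFABP statement has a different fault. Its percentage does not follow from its inputs and its units do not agree, so a reader cannot tell which number is wrong.

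**Working it through.** **Method.** Two-sample comparison of means, 1:1, equal SD. Standardised difference d = difference / SD. Noncentrality = d × √(n/2), with n per group; for n = 20, √10 = 3.162. Power comes from the noncentral t with 38 degrees of freedom. The normal approximation is Φ(noncentrality − z), with z = 1.960 (two-sided 5%) or 1.645 (one-sided 5%).

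**Calibration on 13.1.2 (level stated).** Inputs: 0.42 kg, SD 0.46 kg, n = 20.
- d = 0.42/0.46 = 0.913; noncentrality = 2.887.
- Two-sided 5%: 80.3% (t). The plan's 80% is reproduced.
- One-sided 5% would give 88.3%.

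**Tryptophan (13.1.5).** Inputs: 30 against 40 umol/l, SD 12 (reading ± as SD), n = 20.
- d = 10/12 = 0.833; noncentrality = 2.635.

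| Test | t | Normal approximation |
|---|---|---|
| One-sided 5% | 82.7% | Φ(2.635 − 1.645) = Φ(0.990) = 83.9% |
| Two-sided 5% | 72.8% | Φ(2.635 − 1.960) = Φ(0.675) = 75.0% |

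- The printed 83% is reproduced by the one-sided t-test only.
- Two-sided, 20 per group gives 80% power for d = 0.909, that is 0.909 × 12 = 10.9 umol/l.
- For 10 umol/l two-sided, 80% needs 24 per group (80.7%) and 83% needs about 26 (83.8%; 25 gives 82.3%).
- An SD of about 10.6 instead of 12 would also give 83% two-sided, but that SD is not stated.

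**iFABP (13.1.4).** Inputs: 4 against 6 ng/ml, SD 1.5 read as ng/ml, n = 20.
- d = 2/1.5 = 1.333; noncentrality = 4.216.
- Two-sided 5%: 98.4% (t), 98.8% (normal). One-sided: 99.4% and 99.5%. None gives 85%.
- Other readings also miss 85%: rank-test efficiency of 0.955 gives 98.0%, a log-scale version with coefficient of variation 1.5/4 = 0.375 gives 93.1%, and two-sided 1% gives 92.7%.
- Taken literally, 1.5 ng/dl is 0.015 ng/ml and power is essentially 100%, so the unit slip does not explain the 85%.
- 85% two-sided needs d = 0.972, so a common SD of 2/0.972 = 2.06 ng/ml.
- With 1.5 in controls and 2.5 in the cow's milk arm, the pooled SD is √((2.25 + 6.25)/2) = √4.25 = 2.06, and power is 84.8%.

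**Side check on the other sections.** At two-sided 5%, a 0.5 SD difference with 24 per group (13.1.1) has about 40% power against the stated figure of over 95%. Five VOCs with SD 10.5 and 40 per group (13.1.3) has about 56% against the stated 85%.

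**The case against.** The best defence of 83% is that 13.1.5 is worded directionally: it expects higher levels with cow's milk protein and speaks of detecting an increase. Under a one-sided 5% test the figure is correct, and two-sided 5% is carried over from a different endpoint. What stands is that sidedness is unstated, and that the authors' use of a one-sided test is an inference from a numerical match. It does not rescue the figure. A directional word in a power sentence does not declare a one-sided test, the hypothesis is about differences, and the only convention stated in 13.1 is two-sided. Even if one-sided was meant, the text must say so.

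On iFABP, the SD is given for control infants only, the data are called skewed, and the quoted ranges widen with level (2–7 at 4 ng/ml, 6–42 at 15 ng/ml). A larger SD in the cow's milk arm is therefore plausible and could produce 85%. This stands. The 98% is conditional on a common SD and should not be put forward as the right value. The endpoint is secondary (8.2.1.3) and the printed figure errs on the cautious side.

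A reader might also infer that the trial's main primary outcome is underpowered because of this error. The documents do not support that. Section 8.1.3.2 does list amino acid profiles as primary for Newcastle, but the protocol summary names only microbiota and body composition as primary outcomes. The recruitment target of at least 100 infants is tied to evaluable stool samples. Tryptophan, moreover, stands in for the planned comparison of totals, so correcting its power does not establish the power of that comparison.

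**Conclusion.** The tryptophan statement is wrong as written under the protocol's only declared test level: about 73% (75% by normal approximation) against the printed 83%, a shortfall of 8 to 10 percentage points. This rests on reading ±12 as an SD, on the same SD in both arms, and on carrying two-sided 5% over from 13.1.2. A larger SD in the cow's milk arm would lower it further: 14 umol/l there, with 12 in controls, gives 66%. It would go too far to say that the protocol chose a one-sided test, because it is silent on this.

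The iFABP statement is internally inconsistent rather than optimistic. The 85% does not follow from the printed inputs, and an input needed to obtain it is missing or misprinted. It does not threaten the sample size.

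Both points deserve correction, with the weight on tryptophan. Neither changes the number of infants to be recruited.

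**What to change.** - **13.1.5:** state two-sided 5% and restate the result as about 73% power for a 10 umol/l difference with 20 per group, or as 80% power for 10.9 umol/l. Add that tryptophan stands in for the planned comparison of total levels, whose power is not established. If a one-sided test was intended, declare and justify it.
- **13.1.4:** correct the SD unit from ng/dl to ng/ml, state the test level, and give the SD that yields 85%: about 2.06 ng/ml common to both arms, or about 2.5 ng/ml in the cow's milk arm with 1.5 in controls. Do not replace 85% with 98%, which depends on equal SDs and approximate normality that the section itself gives reason to doubt.
- **13.1.1 and 13.1.3:** do not attach two-sided 5% to these sections by a blanket sentence. Their stated powers fail at that level and would need recomputing at the same time.

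The cost is wording only, with no change to sample size or procedures. The tryptophan figure becomes less favourable.
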